3. STUDY DESIGN

We aim to answer our research questions by conducting a single-centre, proof of concept interventional matched cohort study.

Main study population

Our newly acquired cohort will be compared with a matched historical control group acquired during an earlier study (30). This large multicentre retrospective cohort developed a prediction model for patients with HCA (N=180, HCA diameter at baseline: 82.0mm (65-100) and follow-up: 65.0mm (56-80) (Median (IQR)). This prediction model estimates the probability of HCA regression to <5cm at 1 and 2 years follow-up (30) with an internally validated c-index of 0.79.

The prediction model the authors developed was translated into a chance assessment tool. Included predictors in this model are: diameter at diagnosis, diameter at first follow-up, dates of diagnosis and first follow-up and HCA-subtype. This chance assessment tool will provide the estimated chance of regression to 0,5 cm at 1-2 years after diagnosis and is currently used in clinical practice at Erasmus University Medical Center. The chance tool is available via <https://hcaprediction.shinyapps.io/calculator/>. This prediction model will also be used for our included patients, as part of standard of care.

Matching to the earlier acquired patient cohort will be based on subject age, use of oral contraceptives, ethnicity, weight, type of HCA, size of HCA and number of lesions at baseline. Matching will be conducted via optimal nearest-neighbor matching on propensity score, in a 1:1 ratio without replacement (63). Examination of the balance on covariates resulting from the matching method will be conducted to determine if matching has been successful.

Study subpopulation

As a nested pilot-study we aim to acquire a small sub-cohort of subjects with a slightly different population base criterium, see chapter 4.1. The inclusion and exclusion criteria will be applied in the same way as in the main study population.

This sub-cohort of subjects will be following study procedures according to the procedure defined for the main study population, as stated in chapter 8. They will also be compared with a matched historical control group, in exactly the same way as the main study population. As we expect that the difference in the population base criterium will be a significant confounder in statistical analysis, analysis of this subgroup will be conducted separately, but will be done according to the procedure defined for the main study population, as stated in chapter 10.

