4. STUDY POPULATION

4.1 Population base

Female subjects with a hepatocellular adenoma of any size, who are receiving consultation at the outpatient clinic of Erasmus MC University Medical Centre in Rotterdam, the Netherlands.

Main study population

Female subjects with a hepatocellular adenoma, who are advised to enter an initial surveillance period of 6 months after diagnosis, after reviewing their case by the multidisciplinary team of experts, including a hepatobiliary surgeon, a hepatologist and a liver radiologist.

Study subpopulation

Female subjects with a hepatocellular adenoma, who after the initial surveillance period of 6 months including the regular treatment advice of losing weight and cessation of use of oral contraceptives, did not or only minimally (5mm) experience a reduction of the size of the HCA. Standard treatment for this subgroup after the 6 months of initial surveillance would consist of an additional surveillance period of 6 months, after which another MRI would be performed to assess the change in size of HCA.

[figure not shown]

Figure 2: Graphical representation of main study population and pilot subpopulation

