4.4 Sample size calculation

We based our sample size calculations on the large multicentre retrospective cohort mentioned earlier study (30). This study calculated a median (IQR) HCA diameter at baseline of 82.0mm (65-100) and at 6-month follow-up of 65.0mm (56-80).

Based on this, considering a relevant effect of 20% difference in mean tumour size after 6 months, we estimated an average additional decrease of 13mm in the intervention group when compared to our earlier collected (30).

With a two-sided alpha set at 0.05, power at 0.95, we calculated that at least 51 subjects are required. Anticipating +/- 10% drop-out, we aim to include 55 participants in this study. We aim to include all study subjects in 1 – 1,5 years.

Since the subpopulation is a pilot study, we did not perform a sample size calculation. For this subpopulation, we hypothesized a sample size of 20 subjects. We estimated that this sample size is large enough to provide a reliable initial answer.

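### The pilot compares early non-responders with historical controls not selected on response and, on the natural reading, observed over an earlier 6-month period

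*Protocol*

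**What the plan says.** Section 4.1 defines two groups. The main population consists of women "who are advised to enter an initial surveillance period of 6 months after diagnosis". The subpopulation consists of women who, after that first period and the usual advice to lose weight and stop oral contraceptives, "did not or only minimally (5mm) experience a reduction of the size of the HCA". Their standard care "would consist of an additional surveillance period of 6 months, after which another MRI would be performed". Section 8.1.1 measures size at inclusion and 6 months after the diet starts, so for the subpopulation the endpoint covers the second 6-month period.

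Section 3 then sets the comparator: "They will also be compared with a matched historical control group, in exactly the same way as the main study population". For the main population, that means propensity-score matching on "subject age, use of oral contraceptives, ethnicity, weight, type of HCA, size of HCA and number of lesions at baseline", "in a 1:1 ratio without replacement". The only change described for the historical cohort (180 patients) is in section 4.4: a median of 82.0 mm at baseline and 65.0 mm at 6-month follow-up.

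Section 3 expects the different entry criterion to be an important confounder and responds by analysing the subpopulation separately. Section 10.1 drops the adjustment for oral contraceptive use in this group, and section 10.2 omits the prediction-tool result. Section 4.4 plans 20 subjects without a calculation and says: "We estimated that this sample size is large enough to provide a reliable initial answer".

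**The concern.** The subpopulation is chosen by its outcome in the first 6 months. The controls are not. Neither the matching list nor the regression model contains earlier response or time since diagnosis, although section 8.1.3 collects time since diagnosis for study subjects. No text restricts the pilot's controls to patients who also failed to shrink, or moves their starting point to the first follow-up scan.

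Separate analysis keeps the subpopulation out of the main comparison but leaves its own controls as they were. Removing the contraceptive covariate does not make the controls non-responders either. If slow early shrinkage predicts slow later shrinkage, the control group will shrink more than these women would have done without the diet. The pilot could then miss, or appear to reverse, a real benefit. Enrolling more women would not remove such a bias.

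**Working it through.** **The plan's own figures.** The target is 20% of the 65 mm follow-up median: 0.20 x 65 = 13 mm. Taking the SD from the 6-month interquartile range, (80 - 56)/1.349 = 17.8 mm, a two-sample t-test with two-sided alpha 0.05 and power 0.95 needs about 50 per group, close to the stated 51. So 17.8 mm is a plausible reading of the plan's SD, although the protocol states none. Both figures belong to the main study; the subpopulation has no stated target.

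**Gap in the qualifying period.** The historical medians differ by 82.0 - 65.0 = 17 mm. Subpopulation women lost at most about 5 mm in the corresponding period. The gap is at least 17 - 5 = 12 mm.

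**Effect on the pilot comparison.** Let c = 17 mm be the control shrinkage, m the shrinkage these women would have had in the second 6 months without the diet (assumed), and d the true additional benefit.

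Apparent difference = (m + d) - c; error in the control value = c - m.

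For m = 0 to 5 mm the control value is 12 to 17 mm too high. The chances below use a two-sided t-test with 20 per group (38 df) and an assumed SD of change of 12 or 17.8 mm. The standard error is SD x sqrt(2/20), that is 3.79 or 5.63 mm. The planned analysis is an adjusted regression, so these chances are approximate.

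| m (mm) | Apparent difference if d = 13 | Chance of significant benefit (SD 12 / 17.8) | Apparent difference if d = 0 | Chance of significant result against the diet (SD 12 / 17.8) |
|---|---|---|---|---|
| 0 | -4 | 0.1% / 0.4% | -17 | 99% / 84% |
| 5 | +1 | 4.4% / 3.7% | -12 | 87% / 55% |
| 10 | +6 | 34% / 18% | -7 | 44% / 23% |
| 17 | +13 | 92% / 61% | 0 | 2.5% / 2.5% |

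The last row is the unbiased case. It requires non-responders to shrink in the second period as much as the whole cohort did in the first.

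**Would suitable controls exist?** The protocol does not say. If control change were normal with mean 17 mm and SD 10 to 20 mm (assumed), the share with at most 5 mm reduction would be Phi((5 - 17)/SD), or 11.5% to 27.4%. That is about 21 to 49 of 180, before requiring a second scan and applying the age and BMI limits.

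**The case against.** - **The starting scan.** A reader might infer that the protocol matches pilot controls at diagnosis. It says only at baseline and never names the baseline scan for a pilot control; Figure 2, captioned as showing the two populations, is not available here. Diagnosis is still the natural reading: the main population starts there, the cohort's prediction model uses diameter at diagnosis and at first follow-up, and the pilot must follow the main study's method. Even with another starting scan, nothing selects controls on earlier response.
- **Contraceptives.** A reader might infer that pilot women have all stopped and that the controls have only just done so. Sections 4.1 and 8.3 record advice to stop, not verified cessation, and no passage says when the controls stopped. Contraceptive use is a matching variable. If it reflects current use, matching could favour controls with no recent withdrawal. This may reduce the bias but leaves earlier response unmatched.
- **Magnitude.** The 17 mm is a difference of whole-cohort medians. It is not the change in 20 controls matched on size, type and weight, and adenomas of any size are eligible. Women selected on one small measured change may also shrink more next time through measurement error alone. These points stand, so the size is uncertain and could be smaller.
- **Scope.** This is a nested pilot of 20, analysed separately. That limits the consequence but does not make the comparison sound. A statistical analysis plan could add detail, but the protocol has not left the comparator open.

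**Conclusion.** The comparator for the subpopulation is wrong as written and should be changed; the problem is confined to the nested pilot. The protocol sets women selected for little or no shrinkage, in their second 6-month period, against patients unselected on response in what is most naturally their first. The probable direction is against the diet.

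The size depends on how much these women would shrink without the diet. At 0 to 5 mm, a true additional 13 mm would appear as -4 to +1 mm; at 10 mm, as about +6 mm. These figures rest on the cohort medians and borrow the main study's target. The documents therefore do not support the stronger reading that the bias equals the whole target effect or that the pilot would show harm: that is one end of an assumed range. Nor do they support any doubt, on this ground, about the main-population comparison or its sample size.

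**What to change.** In section 3, replace the instruction to proceed exactly as in the main study with a separate control definition for the subpopulation:

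- eligible controls are historical patients with at most 5 mm reduction at first follow-up;
- time zero and all matching covariates, including diameter, are taken at that scan;
- the control outcome is the change over about the next 6 months;
- the number of such patients with a usable second scan is stated.

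Selecting controls by the same qualifying scan also makes regression to the mean more comparable between the groups. If there are too few, report the subpopulation as a single-arm descriptive pilot with a confidence interval and no control comparison. In section 4.4, remove the claim of reliability.

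The cost is a wording change and a new extraction from the historical cohort. The drawback is a smaller control pool, of undocumented size, which may be tight for 1:1 matching of 20 women.

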4. STUDY POPULATION

4.1 Population base

Female subjects with a hepatocellular adenoma of any size, who are receiving consultation at the outpatient clinic of Erasmus MC University Medical Centre in Rotterdam, the Netherlands.

Main study population

Female subjects with a hepatocellular adenoma, who are advised to enter an initial surveillance period of 6 months after diagnosis, after reviewing their case by the multidisciplinary team of experts, including a hepatobiliary surgeon, a hepatologist and a liver radiologist.

Study subpopulation

Female subjects with a hepatocellular adenoma, who after the initial surveillance period of 6 months including the regular treatment advice of losing weight and cessation of use of oral contraceptives, did not or only minimally (5mm) experience a reduction of the size of the HCA. Standard treatment for this subgroup after the 6 months of initial surveillance would consist of an additional surveillance period of 6 months, after which another MRI would be performed to assess the change in size of HCA.

[figure not shown]

Figure 2: Graphical representation of main study population and pilot subpopulation

4.2 Inclusion criteria

- Age 18-50 years
- BMI > 25 kg/m²
- Provide written consent

4.3 Exclusion criteria

A potential subject who meets any of the following criteria will be excluded from participation in this study:

- Current pregnancy or breastfeeding
- Diabetes Mellitus type 1 or 2
- Insufficient understanding of the Dutch language
- Participation in another clinical study

4.4 Sample size calculation

We based our sample size calculations on the large multicentre retrospective cohort mentioned earlier study (30). This study calculated a median (IQR) HCA diameter at baseline of 82.0mm (65-100) and at 6-month follow-up of 65.0mm (56-80).

Based on this, considering a relevant effect of 20% difference in mean tumour size after 6 months, we estimated an average additional decrease of 13mm in the intervention group when compared to our earlier collected (30).

With a two-sided alpha set at 0.05, power at 0.95, we calculated that at least 51 subjects are required. Anticipating +/- 10% drop-out, we aim to include 55 participants in this study. We aim to include all study subjects in 1 – 1,5 years.

Since the subpopulation is a pilot study, we did not perform a sample size calculation. For this subpopulation, we hypothesized a sample size of 20 subjects. We estimated that this sample size is large enough to provide a reliable initial answer.

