10.1 Primary study parameter

The primary endpoint is the reduction in size (in cm) of the largest diameter of the largest hepatocellular adenoma after 6 months, compared to our matched historical controls. A multivariable linear regression model will be used to estimate the difference in tumour regression between the treatment group and the historical control group. The model will be adjusted for age, change in body weight, the ketogenic diet and oral contraceptive use at baseline.

Subpopulation: the same model will be constructed but will not be adjusted for oral contraceptive use at baseline.

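### Section 4.4: 55 enrolled with 10% drop-out falls short of the required 51, and the 95% power is not shown for the primary analysis, the reduction in diameter

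*Protocol*

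**What the plan says.** Section 4.4 starts from the historical cohort's diameters: median 82.0 mm (IQR 65 to 100) at baseline and 65.0 mm (IQR 56 to 80) at 6 months. The effect is set by "considering a relevant effect of 20% difference in mean tumour size after 6 months", and from this "we estimated an average additional decrease of 13mm in the intervention group". Then: "With a two-sided alpha set at 0.05, power at 0.95, we calculated that at least 51 subjects are required". And: "Anticipating +/- 10% drop-out, we aim to include 55 participants in this study". No SD, SD of change, correlation or test is given, and the text does not say whether 51 is a group size or a total.

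Section 10.1 defines the outcome: "The primary endpoint is the reduction in size (in cm) of the largest diameter of the largest hepatocellular adenoma after 6 months", compared with matched historical controls. The linear model is adjusted for age, weight change, diet and baseline oral contraceptive use. Baseline diameter is not among the covariates. It is one of the variables in the 1:1 propensity-score matching described in section 3.

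Section 8.5 replaces subjects who are withdrawn before starting the diet or who opt out. Section 8.4.1 withdraws subjects with severe symptoms or pregnancy, and section 8.6 keeps those who stop the diet in follow-up.

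**The concern.** There are two separate difficulties in one paragraph.

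First, the enrolment target does not deliver the stated minimum at the stated drop-out rate.

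Second, a power figure belongs to one outcome, one SD and one model. The only spread quoted in section 4.4 is that of diameters at single time points, while the primary analysis is of a change. The SD of a change depends on both spreads and on the correlation between baseline and follow-up, which the protocol does not give. If that correlation is modest, the change is more variable than the 6-month diameter alone and 95% would not hold for the model in section 10.1. A null result would then be read against a power that has not been demonstrated.

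**Working it through.** **Inputs.** From section 4.4: two-sided alpha 0.05, power 0.95, difference 13 mm (0.20 × 65 mm), drop-out 10%, 55 enrolled. From section 3: 1:1 matching. Assumed: SD = IQR/1.349 (normality), and baseline/follow-up correlation r from 0.3 to 0.9, since the protocol gives neither an SD nor a correlation.

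**Implied SDs.** Baseline: (100 − 65)/1.349 = 25.9 mm. Six months: (80 − 56)/1.349 = 17.8 mm.

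**Reproducing 51.** Two-sample t-test, difference 13 mm, 95% power:
- SD 17.8 mm: 49.7 per group, so 50 (normal approximation: 49).
- SD 18 mm: 50.8 per group, so 51.
- Working backwards, 51 per group at 95% power implies an SD of 18.0 mm.
- The baseline SD of 25.9 mm in a two-sample comparison needs 104 to 105 per group. In a one-sample comparison it needs 52 to 54, which is near 51 but again uses the SD of a diameter.

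So 51 fits as a group size with an SD of about 18 mm. Read as a total (25.5 per group), it would give only about 72% power.

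**Drop-out.** 55 × 0.9 = 49.5, so 49 complete. To keep 51: 51/0.9 = 56.7, so 57. The loss that 55 can absorb is 1 − 51/55 = 7.3%. With SD 17.8 mm, power (t) is 95.5% at 51 per group and 94.7% at 49; with SD 18 mm, 95.1% and 94.3%. The slip costs under 1 point.

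**Power for the reduction in diameter, 51 per group, 13 mm.**
- SD of change = √(25.9² + 17.8² − 2r × 25.9 × 17.8).
- Baseline-adjusted residual SD = 17.8 × √(1 − r²).
- Unmatched: two-sample t-test on the change.
- Exact matching on baseline diameter, analysed unpaired: the test uses SE = SD of change × √(2/51), but the group difference varies only with the residual SD. Power = Φ[(13 − 1.984 × SD of change × √(2/51)) / (residual SD × √(2/51))]. At r = 0.5 this is Φ[(13 − 9.03)/3.05] = Φ(1.30), about 90%.

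| r | SD of change (mm) | Unmatched | Exact matching, unpaired | Residual SD (mm) | Baseline-adjusted |
|---|---|---|---|---|---|
| 0.3 | 26.7 | 68% | 77% | 17.0 | 97% |
| 0.5 | 23.0 | 81% | 90% | 15.4 | 99% |
| 0.6 | 20.9 | 88% | 96% | 14.2 | >99% |
| 0.7 | 18.5 | 94% | 99% | 12.7 | >99% |
| 0.8 | 15.8 | 98% | >99% | 10.7 | >99% |
| 0.9 | 12.6 | >99% | >99% | 7.8 | >99% |

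Unmatched, 95% is reached at r of about 0.72; with exact matching, at about 0.6. None of these figures allows for the other covariates in section 10.1.

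**The case against.** The strongest reply has four parts.

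- **The SD is inferred.** A reader might conclude that the calculation was done on the wrong variable. The protocol does not support that as fact. It states no SD and words the 13 mm as an additional decrease, and a change SD of 18.0 mm (r about 0.72 on these SDs) would give the same 51. For groups balanced at baseline, 13 mm is the same contrast on either scale. This stands. What can be said is that the SD and its source are missing, and that 51 matches the 6-month spread.
- **The low figures ignore matching.** Baseline size is a matching variable, so the unmatched column is the unfavourable end. This stands too, in part: propensity-score matching balances groups overall and need not pair diameters closely, so the truth lies between the two columns, and analysing the pairs as pairs would raise power further.
- **Normality is doubtful.** The 6-month quartiles lie 9 mm below and 15 mm above the median. The SDs are approximations.
- **The drop-out slip is trivial.** The 10% is stated loosely, section 8.5 replaces opt-outs, and section 8.6 keeps diet non-completers in follow-up. That reduces the consequence, but section 8.5 does not provide for replacing subjects withdrawn after starting for severe symptoms or pregnancy, and the three numbers in section 4.4 still do not agree.

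That 51 refers to the diet group is a fair reading, since every enrolled subject receives the diet (section 8.2) and the controls are historical. It remains a point of wording.

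**Conclusion.** Section 4.4 is inconsistent as written: 51 required, 10% drop-out and 55 enrolled cannot all hold. The shortfall is about two participants and under 1 point of power on the inputs that reproduce 51.

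The 95% power is not shown for the analysis in section 10.1. Under IQR-derived SDs, power for the change runs from about 68% (r = 0.3, no matching) to above 99% (r = 0.9), depending on a correlation and a match quality that the protocol does not give. A reader might infer that the study is underpowered. The document does not establish that: at r of 0.8 power exceeds the stated figure even without matching, and close matching lowers the correlation needed. The finding is an unsupported power statement and an arithmetic slip, not a demonstrated lack of power.

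**What to change.** In section 4.4:
- State the SD used and its source, taking the SD of the 6-month change and the baseline/follow-up correlation from the historical cohort.
- Write 51 participants and 51 matched controls.
- Restate the drop-out allowance as about 7%, or keep 10% and give the power at 49 evaluable (about 94% to 95% on the reconstructed inputs).

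In section 10.1, add baseline diameter to the primary model, and quote power in section 4.4 for that model. Under the assumptions above it is about 97% or more for every r from 0.3 to 0.9.

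The cost is a rewritten paragraph, one covariate that is already collected, and a short calculation on existing data. No additional patients are needed.

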5. TREATMENT OF SUBJECTS

5.1 Investigational product/treatment

All subjects will receive a diet for 6 months (see table 1 & 2 for the example diet). In this ketogenic diet the amount of carbohydrates is restricted, the first three months to approximately 35 grams per day, the second part for month 4-6 to approximately 60 grams per day. This amount of carbohydrates will lead to ketogenesis. Emphasis is placed on the use of products high in polyunsaturated and monounsaturated fatty acids (diet margarines, oils, fish, nuts), preferably with vegetable and marine sources of protein, in concordance with the national nutritional guidelines (64). We aim to moderately reduce the calories to about 70-80% of the daily energy requirements.

After the study period of 6 months, participants are free to choose which diet they want to follow. They can choose to keep following the moderate carbohydrate restricted diet, or switch to a diet according to the national nutrition guidelines. If they would like advice from a dietician, they can be referred to a dietician via their family doctor.

After participating in this study, subjects will receive further treatment according to standard clinical practice: they will be included in regular follow-up or undergo treatment for their HCA. The frequency of follow-up or possible invasive treatment depends on the findings on the MRI made after six months and the calculated chance of regression, according to current protocol.

Diet Overview:

Month 1-3: Low carbohydrate, ketogenic diet containing approximately 1500 kcal, 35 grams of carbohydrate and 0.8 g/kg of protein /day

Month 4-6: Moderate carbohydrate, ketogenic diet containing approximately 1500 kcal, 60 grams of carbohydrate and 0.8 g/kg of protein /day

